# 8.7. Vital Signs Recorded Over the Course of the Study

Vital signs will include blood pressure and heart rate and be presented using the Level 3 table format. Data will be summarized and reported in Table 14.1.7 entitled *Summary of the Vital Sign Results* (ITT population) using the Level 3 table design; Table 14.1.7a will be restricted to the FAS population. Listing 16.4.10 entitled *Vital Sign Results* provides supportive data for Tables 14.1.7 and 14.1.7a and will be sorted by site number, and patient number.

### 9. ENDPOINTS ANALYSES

There is a single primary endpoint and 18 secondary endpoints. Based on the feasibility nature of this study, there are no formal hypothesis tests.

### **Primary Endpoint**

The primary endpoint of the study is predicated on safety; the distribution of this endpoint is binary. The primary population for analysis of this endpoint will be the ITT population.

Proportion of patients experiencing one or more device- or procedure-related serious adverse events at 12 weeks post-procedure.

All device-related or procedure-related serious adverse events from the start of the study procedure through relative study day 84 will be used in the tabulation.

The secondary endpoints are listed below:

### **First Secondary Endpoint**

The distribution of this endpoint is binary. The primary population for analysis of this endpoint will be the FAS population.

Procedure success: defined as successful treatment of at least 6 cm of duodenum segment.

Immediately following the study procedure, a determination will be made regarding treatment of  $\geq 6$  cm of the duodenum. Patients who fail to have  $\geq 6$  cm of the duodenum treated, for any reason, will be counted as not having achieved **Procedure Success**.

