12.3 Analysis Populations

The following analysis populations are defined for the study: Intent-to-Treat (ITT), modified Intent-to-Treat (mITT), Per-Protocol (PP) and Completed Cases (CC). The primary safety analysis will be performed on the ITT population. The primary effectiveness analysis will be performed on mITT population.

- Intent-to-Treat: The Intent-to-Treat population includes all enrolled participants as defined in Section 5.3 regardless of whether or not the participant received the full treatment.
- Modified Intent-to-Treat: The mITT population consists of the ITT population participants who received the target treatment (at least 6 cm of duodenum treatment) and that have at least one post-treatment follow-up.
- Per-Protocol: The Per-Protocol population is a subset of the mITT population and includes all participants who received the target treatment (at least 6 cm of duodenum treatment), have at least one post-treatment follow-up, do not have any major eligibility violations, and maintained stable glucose-lowering medications for 24 weeks post procedure.

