12.4.4 Effectiveness Analysis

Secondary endpoints are summarized in Section 3. The primary analysis of the study's secondary endpoints will be performed using the mITT population. The analysis will also be performed using the PP population when appropriate.

Results for these endpoints will be tabulated and reported for each treatment arm at each timepoint for which data were specified to be collected, using change scores from baseline where appropriate. For binary outcomes, Fisher's exact test will be used to assess differences which may be present between groups, while t-tests or Wilcoxon's rank-sum will be applied for continuous outcomes depending on the normality assumption. Effectiveness endpoints collected at multiple timepoints post-intervention (e.g., HbA1c) will also be assessed longitudinally using repeated-measures mixed-effects models with time as the repeated measure and treatment arm as a factor variable. Assessment of overall change from baseline and comparisons between treatment arms will then be predicated principally upon these repeated-measures analyses.

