### 6. ANALYSIS POPULATIONS

Patients will be considered enrolled in the study once the patient has passed endoscopic screening. Screen failures are defined as patient who consented to participate in the clinical study and started the screening tests specified by the protocol but are not subsequently enrolled in the study.

The primary and secondary safety analyses will be performed using the ITT. The primary effectiveness analyses will be performed using the FAS population. The Per-Protocol population and Completed-Cases population will be used for the sensitivity analyses of the primary and secondary effectiveness endpoints.

*Intent-to-Treat*: The Intent-to-Treat population includes all enrolled patients, regardless of the patient having received the target treatment (at least 6cm of duodenum treated). The point of enrollment occurs when a patient has provided written informed consent and an energy delivery has been attempted during the index procedure.

*Full Analysis Set*: The FAS population consists of the ITT population patients who received the target treatment (at least 6 cm of duodenum treatment) and that have at least one post-treatment follow-up examination.

**Per-Protocol**: The Per-Protocol population is a subset of the FAS population and includes all patients who received the target treatment, do not have any major eligibility violations, and maintained stable glucose-lowering medications for 24 weeks post-procedure. The definition of what constitutes a major eligibility violations will be established before the study database is locked.

**Completed Cases**: The Completed Cases population is a subset of the Per-Protocol population and includes all patients who received the target treatment, do not have any major eligibility violations, and maintained stable glucose-lowering medications for 24 weeks post-procedure, and completed the final Week 48 End of Study Visit.

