### 7. GENERAL CONSIDERATIONS

Post-text Tables and Listings will be prepared in accordance with the current ICH Guidelines. The header of each Table and Listing will include the sponsor's name and the study number. The information and explanatory notes to be provided in the "footer" or bottom of each Table and Listing will include the following information:

- 1. Date and time of output generation.
- 2. SAS® program name, including the path that generates the output.
- 3. Any other output specific details that require further elaboration.

In general, tables will be formatted with a column displaying findings for all patients combined. Row entries in tables are made only if data exist for at least one (1) patient (*i.e.*, a row with all zeros will not appear). The only exception to this rule applies to tables that list the termination status of patients (*e.g.*, reasons for not completing the study). In this case, zeros will appear for study termination reasons that no patient satisfied. The summary tables clearly indicate the number of patients to which the data apply, and unknown or not performed are distinguished from missing data. Tables, Listings, and Figures will provide the units of measurement, unless there are no units. Results recorded at single times during the study will be presented using the *Level 1* displays for the ITT Population; the example structure is presented below.

Level 1a Display

Parameter	Device Generation 1 / 600	Device Generation 1 / 600	Device Generation 2 / 750	All
and Statistic	Volts / Single Treatment	Volts / Double Treatment	Volts / Double Treatment	Patients
Age				
Sex				

Level 1b Display

		zever re zaspawy	
	Device Generation 1 / 600 Volts	Device Generation 1 / 600 Volts / Double	All
Parameter and Statistic	/ Single Treatment	Treatment and Device Generation 2 / 750 Volts /	Patients
		Double Treatment	
Age			
Sex			

The Level 2 displays will be used for summarizing the incidence of AEs. An example of the layout for AEs by severity is presented below.

Level 2a Display

System Organ Class	Device Generation 1 / 600	Device Generation 1 / 600	Device Generation 2 / 750	All
Preferred Term	Volts / Single Treatment	Volts / Double Treatment	Volts / Double Treatment	Patients
SOC				
PT				

Level 2b Display

System Organ Class	Device Generation 1 / 600 Volts	Device Generation 1 / 600 Volts / Double Treatment and Device Generation 2 / 750 Volts / Double Treatment	All
Preferred Term	/ Single Treatment		Patients
SOC PT			

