### **Binary Variable Assessed at a Single Time Point (3 endpoints):**

- **Secondary Endpoint:** Procedure success: defined as successful treatment of at least 6 cm of duodenum segment.
- **Secondary Endpoint:** Proportion of treated patients with an HbA1c improvement of  $\geq 0.5\%$  from baseline at 24 weeks (24 week score minus baseline score).
- **Secondary Endpoint:** Proportion of treated patients with an HbA1c improvement of >0.5% from baseline at 24 weeks maintained at 48 weeks.

For each set of results for each Comparison Set, the following 2 research questions will be addressed. Results will be presented using the Level 1 tables b through e.

For the endpoints measured on a binary scale, what are the overall estimates in the FAS population.

For the endpoints measured on a binary scale, is there a difference in the estimates in the FAS population based on the generation of the device, voltage, and single vs. double treatment?

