### **Continuous Variable Assessed at Multiple Time Points (11 endpoints):**

- **Secondary Endpoint:** Change from baseline (post-baseline minus baseline) in HbA1c reported for each pre-specified study visit.
- **Secondary Endpoint:** Change from baseline (post-baseline minus baseline) in Fasting plasma glucose (FPG) reported for each pre-specified study visit.
- **Secondary Endpoint:** Change from baseline (post-baseline minus baseline) in Insulinresistance by HOMA-IR reported for each pre-specified study visit.
- **Secondary Endpoint 6a:** Change from baseline (post-baseline minus baseline) in Post-prandial plasma glucose (PPG) reported for each pre-specified study visit.
- **Secondary Endpoint 6b:** Change from baseline (post-baseline minus baseline) in beta cell function reported for each pre-specified study visit.
- **Secondary Endpoint 6c:** Change from baseline (post-baseline minus baseline) in disposition index reported for each pre-specified study visit.
- **Secondary Endpoint:** Change from baseline in blood pressure by visit.
- Secondary Endpoint: Change in lipid profile from baseline by visit: total cholesterol
- Secondary Endpoint: Change in lipid profile from baseline by visit: triglycerides

- Secondary Endpoint: Change in lipid profile from baseline by visit: HDL
- Secondary Endpoint: Change in lipid profile from baseline by visit: LDL
- Secondary Endpoint: Change in weight from baseline (post-baseline minus baseline) by visit. Weight will be evaluated based on the intra-patient percent change from baseline. (% TBWL: % Total Body Weight Loss)
- Secondary Endpoint: Time in Range (TIR) based on Continuous Glucose Monitoring (CGM) by visit

For each set of results for each Comparison Set, the following 2 research questions will be addressed. Results will be presented using the Level 3 tables b through e.

For each endpoints measured on a continuous scale, what are the overall estimates in the FAS population assessed over time.

For each endpoint measured on a continuous scale, is there a difference in the estimates in the FAS population based on the generation of the device, voltage, and single vs. double treatment assessed over time?

The list of the top-line tables to be generated are presented below:

Table 14.4.1 entitled Overall Summary of Procedure Success and Procedure Time (FAS Population)

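### Procedure success (at least 6 cm treated) is analysed in a population that admits only patients with at least 6 cm treated, so the result is 100% by construction

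*SAP*

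**What the plan says.** Protocol section 3 and SAP section 9 both define procedure success as treatment of 6 cm or more of duodenum. It is one of two endpoints serving the technical-feasibility objective; the other is procedure time.

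The SAP assigns it to the Full Analysis Set in three places:

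- SAP 9, First Secondary Endpoint: "The distribution of this endpoint is binary. The primary population for analysis of this endpoint will be the FAS population".
- SAP 9.2, binary endpoints at a single time point: "For the endpoints measured on a binary scale, what are the overall estimates in the FAS population".
- SAP 9.2, list of top-line tables: "Overall Summary of Procedure Success and Procedure Time (FAS Population".

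The protocol has the same structure. Section 12.4.4 states that the primary analysis of the "secondary endpoints will be performed using the mITT population", and SAP section 3 says that the FAS is the protocol's mITT.

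The entry rules are:

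- SAP 6: "The FAS population consists of the ITT population patients who received the target treatment (at least 6 cm of duodenum treatment", with at least one post-treatment follow-up examination also required.
- Protocol 12.3: "mITT population consists of the ITT population participants who received the target treatment (at least 6 cm of duodenum treatment", again with at least one follow-up.

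Two other SAP statements point towards a wider population. The First Secondary Endpoint text says that patients with less than 6 "cm of the duodenum treated, for any reason, will be counted as not having achieved" procedure success. SAP 7 sends results recorded at a single time to Level 1 "displays for the ITT Population; the example structure is presented below".

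**The concern.** The condition for entering the FAS is the event being measured. A patient with less than 6 cm treated leaves the denominator instead of counting as a failure, so the planned estimate carries no information about how often the procedure succeeds.

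Failures are foreseeable under the plan. Both documents define the ITT population to include patients regardless of whether the full or target treatment was received, and Protocol 5.3 enrols at attempted catheter insertion, before any length has been treated.

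Feasibility is part of the study's stated objective. SAP 9.2 also asks whether the binary endpoints differ by device generation, voltage and single versus double treatment. With every group fixed at 100%, neither Comparison Set can answer that for procedure success. A reader of the planned table could not tell an achieved 100% from a guaranteed one.

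**Working it through.** **Inputs**

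- Success: at least 6 cm treated (Protocol 3; SAP 9).
- FAS/mITT: at least 6 cm treated and at least one follow-up (SAP 6; Protocol 12.3).
- Per-Protocol is a subset of the FAS, and Completed Cases a subset of Per-Protocol (SAP 6).
- Group sizes: 3 (Generation 1, 600 V, single), 7 (Generation 1, 600 V, double) and 10 (Generation 2, 750 V, double). Total 3 + 7 + 10 = 20; pooled double treatment 7 + 10 = 17 (SAP 3; SAP 7, Comparison Sets).
- Exact confidence intervals for single proportions (SAP 7).
- The plan states no expected success rate, so there is no figure to reproduce.

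**Step 1: the rate in the FAS.** Let S be the number of patients with at least 6 cm treated and at least one follow-up. The FAS contains exactly those S patients and all are successes, so the rate is S/S = 100%. The same holds in every subset, so the Per-Protocol and Completed Cases sensitivity analyses are also 100%. The follow-up condition also drops any technical success who never returned.

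**Step 2: the failure rule.** SAP 9 counts less than 6 cm treated as failure. FAS membership requires at least 6 cm. No patient can satisfy both, so the rule has nobody to act on.

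**Step 3: size.** The documents give no failure count, so the number of failures k is assumed and follow-up is taken as complete. The exact (Clopper-Pearson) 95% limits for x successes in n are:

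- lower = 2.5% quantile of Beta(x, n − x + 1);
- upper = 97.5% quantile of Beta(x + 1, n − x), or 1 when x = n;
- when x = n the lower limit is 0.025^(1/n), for example 0.025^(1/19) = 82.4%.

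| Assumed failures | All enrolled | FAS |
|---|---|---|
| k = 0 of 20 | 20/20 = 100% (83.2–100) | 20/20 = 100% (83.2–100) |
| k = 1 of 20 | 19/20 = 95.0% (75.1–99.9) | 19/19 = 100% (82.4–100) |
| k = 2 of 20 | 18/20 = 90.0% (68.3–98.8) | 18/18 = 100% (81.5–100) |

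One assumed failure placed within each SAP group:

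| Group | All enrolled | FAS |
|---|---|---|
| Gen 1, 600 V, single (3) | 2/3 = 66.7% (9.4–99.2) | 2/2 = 100% (15.8–100) |
| Gen 1, 600 V, double (7) | 6/7 = 85.7% (42.1–99.6) | 6/6 = 100% (54.1–100) |
| Gen 2, 750 V, double (10) | 9/10 = 90.0% (55.5–99.7) | 9/9 = 100% (66.4–100) |
| Pooled double (17) | 16/17 = 94.1% (71.3–99.9) | 16/16 = 100% (79.4–100) |

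**Step 4: group comparison.** Protocol 12.4.4 names Fisher's exact test for binary outcomes. To show the mechanism at its extreme, suppose 5 of 10 fail at 600 V and none at 750 V. All enrolled gives 5/10 vs 10/10, two-sided p = 0.033. The FAS gives 5/5 vs 10/10, p = 1.0. In the FAS, p = 1.0 for any failure pattern that leaves patients in both groups.

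**The case against.** The strongest reply is that failures would not be hidden. SAP 8.1 plans a patient accounting by analysis population, SAP 8.4 summarises index-procedure details in the ITT population (Table 14.1.4), and SAP 7 lists all data. With no formal hypothesis tests, the line between descriptive output and endpoint analysis is thinner than usual. This stands in part: a careful reader might find a failure there. But ITT size minus FAS size only bounds the failures, because patients without follow-up also drop out, and none of these outputs is the analysis of procedure success.

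Second, the SAP 7 statement about ITT displays is a general layout rule with age and sex as its example rows. SAP 8 also uses Level 1 tables for the FAS, and SAP 9.2 puts its other single-time endpoints in the FAS too. That is fair. The departure from SAP 7 is secondary support only; the firm contradiction is inside the First Secondary Endpoint text itself.

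Third, counting from attempted catheter insertion may seem to create a new analysis set, because the ITT definition in SAP 6 refers to attempted energy delivery. It is, however, the protocol's own ITT (sections 5.3 and 12.3), and SAP 5.1 repeats that point of enrolment. The difference matters here: a patient with insertion attempted and no energy delivered is a clear technical failure.

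Finally, there may be no failures at all. In that case the number does not change, but the planned analysis could not have shown anything else.

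**Conclusion.** The concern holds. As written, procedure success is 100% overall, in every group of both Comparison Sets and in both sensitivity populations, by definition and not by result. This follows from the two definitions alone and needs no assumption.

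The numerical effect does rest on assumed failures. With one or two among 20 and complete follow-up, the reported rate overstates the all-enrolled rate by 5 or 10 percentage points. A single failure in the group of three changes that group's figure from 66.7% to 100%. With no failures and complete follow-up the two analyses coincide.

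The point should be fixed but is not critical. The endpoint is secondary, has no success threshold and does not enter the stopping rules in Protocol 4.5. The primary safety endpoint is analysed in the ITT population and is not affected by this assignment.

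**What to change.** Change the population for this one endpoint in SAP 9 (First Secondary Endpoint), SAP 9.2 (binary endpoints), the title of the Procedure Success and Procedure Time table, and Protocol 12.4.4:

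- Analyse procedure success in all enrolled patients, with the denominator fixed at the protocol's point of enrolment, attempted catheter insertion.
- Count every patient with less than 6 cm treated as a failure, as SAP 9 already says.
- Report exact 95% intervals overall and for the SAP's groups (3, 7 and 10; 3 versus 17), and state in which group a patient with no energy delivered is counted.
- Keep the FAS for the glycemic endpoints.

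Two edits follow. The planned table combines procedure success with procedure time under one FAS label, so it must be split or carry two populations. Procedure time is also restricted to the FAS, so the SAP should say whether procedures that treated less than 6 cm are meant to be left out.

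The SAP describes enrolment or the ITT population in different ways: passing endoscopic screening, with or without proceeding to the index procedure (sections 3 and 6); attempted energy delivery (3 and 6); attempted insertion (5.1); and initiation of endoscopic screening (10). These should be reconciled as a separate item, because that choice also alters the primary safety population. The change proposed here leaves the ITT definition alone.

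The cost is wording in four places. No new data are needed, since SAP 9 already requires the 6 cm determination immediately after the procedure. The protocol edit needs the approvals described in Protocol 15.1. The reported success rate may fall below 100%.

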### **Second Secondary Endpoint**

The distribution of this endpoint is continuous. The primary population for analysis of this endpoint will be the FAS population.

Procedure time: defined as the time between the Endogenex catheter insertion and the catheter removal.

Procedure Time will be reported in minutes.

### **Third Secondary Endpoint**

The distribution of this endpoint is continuous. The primary population for analysis of this endpoint will be the FAS population.

Change from baseline (post-baseline minus baseline) in HbA1c reported for each pre-specified study visit.

The pre-specified study visits where HbA1c is recorded is Week 4, 12, 24, 36, 48.

### **Fourth Secondary Endpoint**

The distribution of this endpoint is continuous. The primary population for analysis of this endpoint will be the FAS population.

Change from baseline (post-baseline minus baseline) in Fasting plasma glucose (FPG) reported for each pre-specified study visit.

The pre-specified study visits where FPG is recorded is Week 4, 12, 24, 36, 48.

### **Fifth Secondary Endpoint**

The distribution of this endpoint is continuous. The primary population for analysis of this endpoint will be the FAS population.

Change from baseline (post-baseline minus baseline) in Insulin-resistance by HOMA-IR reported for each pre-specified study visit.

The pre-specified study visits where HOMA-IR is recorded is Week 4, 12, 24, 36, 48.

### Sixth Secondary Endpoint 6a

The distribution of this endpoint is continuous. The primary population for analysis of this endpoint will be the FAS population. The estimates will be derived using a mixed model repeated measure procedure; the 12 week result will be the principal time point of interest.

Change from baseline in glycemic parameters [Post prandial plasma glucose (PPG) by mixed meal tolerance test (MMTT)] post index procedure, by visit

#### Sixth Secondary Endpoint 6b

The distribution of this endpoint is continuous. The primary population for analysis of this endpoint will be the FAS population. The estimates will be derived using a mixed model repeated measure procedure; the 12 week result will be the principal time point of interest.

Change from baseline in glycemic parameters [Beta cell function by mixed meal tolerance test (MMTT)] post index procedure, by visit

#### Sixth Secondary Endpoint 6c

The distribution of this endpoint is continuous. The primary population for analysis of this endpoint will be the FAS population. The estimates will be derived using a mixed model repeated measure procedure; the 12 week result will be the principal time point of interest.

Change from baseline in glycemic parameters [Disposition Index (DI) by mixed meal tolerance test (MMTT)] post index procedure, by visit

The pre-specified study visits where PPG is recorded is Week 4, 12, 24, 36, 48.

